This is a prospective placebo-controlled randomized study. Patients will enter with active disease. After informed consent and screening procedures are completed, enrolled patients may be optionally treated with intramuscular methylprednisolone acetate and background immune-suppressive medications will be withdrawn. Injection of methylprednisolone acetate may be repeated in week 2 at the discretion of the investigator, to induce a state of remission/low disease activity. Patients will be assigned to begin the study medication upon enrollment (baseline, week 0). Patients will be randomized 1:1 to Aggrenox or half of an 81mg aspirin tablet twice daily for 24 weeks. Aggrenox will be initiated at a single bedtime dose for a week, followed by twice daily administration for the rest of the study, to minimize the risk of side effects (e.g. dizziness, headache). Aspirin will be titrated similarly to preserve blinding. Gelatin capsules will be used to cover the pills in order to preserve the blinding.

Participants will be evaluated at baseline (week 0), week 2, week 4 and every 4 weeks until the completion of the study at week 24. An additional study visit may be scheduled at the time of a clinically significant flare (flare visit). Evaluation of general health status, adverse events and lupus disease activity (SLEDAI, BILAG, PGA, CLASI, DIAL, SF-36v2, Lupus QoL, FACIT-fatigue, PSQI, CES-D) will be performed at baseline, week 4 and every subsequent visit. Time to first flare and severity of first flare will be examined. At the time of a clinically significant flare

(defined as at least one BILAG letter grade increase or an increase of ≥ 3 points in SLEDAI AND clinician determination of clinically significant deterioration) patients may elect further treatment with intramuscular methylprednisolone acetate or, if necessary DMARD therapy, but will continue the study as permanent nonresponders.

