Data will be collected by study personnel who will be kept blinded to treatment assignments. A trained study coordinator will provide data monitoring and quality assurance checks on the database. The final data will be pooled and analyzed by the investigators.

E. Statistical methods

The primary analysis will be an intention-to-treat two by two table.

Primary endpoint: A two by two table analysis of rate of response by the BICLA response index at week 24 compared to baseline (week 0) in patients on aspirin versus Aggrenox regimens, with non-response attributed to patients who receive defined non-responder treatments and/or withdraw early. Please see below for power calculations based on expected response rates. Independent predictors of BICLA response, including baseline biomarkers, biomarker responses to Aggrenox treatment, demographics and amount of steroids administered, will be further investigated by exploratory logistic regression modeling.

Secondary endpoints: Flare rates at week 24 compared between completers among treatment groups. Time to flare (log rank test). SRI 4/5 at week 24, BICLA and SRI 4/5 at each month. HRQOL comparing treatment groups versus baseline at week 24 and at each month. Although our primary endpoint is based on the BICLA response, an accepted outcome for lupus clinical trials which serves as a pilot response indicator for future trials, it is likely that some secondary endpoints, such as time to flare will be more sensitive, and more likely to achieve significance in a pilot study.

Exploratory endpoints: SRI component analyses and CLASI responses. Refinement in BICLA and SRI analysis using a propensity score derived by multiple potential confounders identified in exploratory single variate analysis. Relation of clinical and biologic endpoints with heart rate variability measures by multivariate analysis.

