Biologic Endpoints: Changes in B cell and T cell subsets, relevant gene expression patterns, B-T cytokine profiles and cell-bound complement split products and urinary biomarkers at baseline versus week 24 in each treatment group. Evaluation of B Cell/T cell expression patterns in patients with higher versus lower IL6, IL17 and IL23 expression detected at baseline. These endpoints will be evaluated both as changes with Aggrenox versus aspirin treatment (non parametric analysis) and as components of multivariate modeling and propensity score analysis as described above. An exploratory responder analysis will also be performed (changes in these biomarkers with response versus non-response in patients receiving Aggrenox). The latter analysis may need to be observational only, as it is likely to be underpowered and diluted by patients who may not have begun the trial with the characteristic abnormalities in T cell subset activity.

Power/Sample size calculation

We base this calculation on preliminary data from the BOLD study (11) which is an exploration of underlying biology in patients with SLE who receive steroids and are withdrawn from background treatments, in other words identical to the aspirin group in the current proposal. To date we have analyzed data from 31 patients who completed the BOLD protocol and these outcomes suggest that no more than 20% of the aspirin group will achieve a BICLA response at week 16 (range 1-20%) and no more than 5% achieves a BICLA response at week 24 (range 0-10%). Assuming a 35 to 50% response rate in the Aggrenox group at week 24, a sample size of 50 patients will provide a power around 80% at a significance level of 0.05 at week 24. By these settings and assumptions, the following power estimates are obtained.

Power calculations for a 50 patient study, if alpha=0.05 with response rates:

	Rate 1	Rate 2	Rate 3	Rate 4	Rate 5	Rate 6	Rate 7
Aggrenox n=25	60%	55%	50%	45%	40%	35%	35%
Aspirin n=25	20%	15%	10%	10%	5%	5%	3%
power	0.84	0.86	0.89	0.80	0.86	0.77	0.84

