An absolute difference of ≥ 12 to 15% in the response rate is however considered clinically significant in other lupus trials. Since this is a pilot study, a clinically significant (12% or greater absolute difference), but not statistically significant difference, might be considered justification for a larger study. Even if this pilot study does not reach statistical significance, the proposed exploratory biomarker studies evaluating T and B cell phenotypes, T/B cell functional studies, gene expression or serum cytokine/chemokine profiles might be used to refine the entry criteria and biologic treatment goals for a further study and/or underscore the rationale for an expansion of this study for more power of discrimination. Finally, the BICLA and other flare analyses will be performed at each monthly visit, increasing the likelihood of finding differences, should they exist, when including these secondary analyses.

An interim analysis will be performed after 20 patients will have completed the study, and will be used to assess the quality of the data collected and the treatment effects. Consideration of sample size changes can be discussed at that time.

F. Gender/Minority/Pediatric Inclusion for Research

Participants will be age 18 or older. Race, minority status and gender will not affect enrollment.

G. Human participants

The study population will include male/female patients with SLE, of age 18 or older and of all races.

Inclusion Criteria:

1. Patients with SLE meeting the ACR Classification Criteria (19)
2. Males or females, age 18-70
3. Evidence of positive ANA or anti-dsDNA within one year of screening
4. SLEDAI ≥ 4 or ≥ 1 BILAG B or A at screening, despite standard of care

Exclusion Criteria

1. WBC $< 2,000/\text{mm}^3$, lymphocytes $< 300/\text{mm}^3$ (last known labs)
2. AST or ALT > 3 times above normal cut off values (last known labs)
3. Acute lupus nephritis defined as class II, III, IV or V nephritis diagnosed within 6 months or prot/creat > 1.5 gm/gm due to active lupus or in process of receiving induction therapy for nephritis
4. Active CNS lupus affecting mental status
5. Pregnancy or breast feeding
6. Current requirement for anticoagulation
7. Contraindication to aspirin or dipyridamole, including history of recent or severe GI bleeding, hemoglobin < 9 mg/dL, platelet count of $< 30,000/\text{mm}^3$ or unstable platelet count (last known labs)

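### The secondary week-24 flare-rate comparison is restricted to completers, so randomisation does not protect it and flares recorded before withdrawal are dropped (minor)

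*Combined protocol and SAP*

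**What the plan says.** Flare rate and time to first flare form the first secondary objective (section A). Under Secondary endpoints, section E states the analysis of the rate as "Flare rates at week 24 compared between completers among treatment groups". The term completer is not defined. Section D describes visits "until the completion of the study at week 24", and the interim analysis counts patients who have completed the study, so I read it as study completers.

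The protection given to the primary endpoint is not extended to this one. Section E says "The primary analysis will be an intention-to-treat two by two table", and the BICLA analysis is made "with non-response attributed to patients who receive defined non-responder treatments and/or withdraw early". No such rule is given for flare rates.

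Three other statements bear on the point:
- A log-rank test of time to flare is also planned. Section E names time to flare as an example of a secondary endpoint likely to be more sensitive than the primary. Its analysis set and censoring rule are not stated.
- The power section adds that "the BICLA and other flare analyses will be performed at each monthly visit".
- Patients who flare may receive further treatment, "but will continue the study as permanent nonresponders" (section D). A flare is therefore not in itself a planned exit from the study.

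The January 2015 amendment interrupts the randomised part and adds an uncontrolled group. It does not change this analysis.

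**The concern.** Randomisation makes the arms comparable at week 0. Patients who reach week 24 are a selected subset, and the selection can differ by arm. Section C itself warns of poor tolerability: in an external stroke trial, 34% stopped treatment for intolerance on dipyridamole plus aspirin against 13% on aspirin alone. If patients who leave this study have a different flare risk from those who stay, and more leave one arm than the other, the completer difference can move away from the truth even when the drug does nothing.

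The rule also wastes data. A patient who flares at week 6 and withdraws at week 14 has an observed flare that this comparison ignores. At stake is a secondary result on the outcome named in the study's title, in a trial of at most 50 patients.

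**Working it through.** **The plan's own figures.** The plan gives no power, expected rate or dropout for the flare-rate comparison. Its only power table concerns BICLA response. A two-sided pooled test with 25 per arm reproduces that table to within 2 points, but it does not bear on this question.

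**Inputs.**
- Flare rate: 100% by week 24 in BOLD, with a first flare at 72 days on average (section C). Section E calls the BOLD population "in other words identical to the aspirin group in the current proposal", so it describes that arm only.
- Aggrenox: 35-50% BICLA response at week 24 (section E). Section A describes response as excluding a new flare, so Aggrenox flaring is at most 1 - 0.50 = 50% to 1 - 0.35 = 65%.
- Withdrawal: not given. As an assumption, *w* = 0.34 and 0.13, the external drug-discontinuation rates; alternatively half of each.
- 25 per arm, the maximum enrolment split 1:1. Completers: 25 × 0.66 = 16.5 and 25 × 0.87 = 21.75.

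**Step 1: bias with equal true rates.** Let *f* be the flare rate in the whole arm and *q* the rate among non-completers. The completer rate is (*f* - *wq*)/(1 - *w*).

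| *f*, both arms | *q* | Aggrenox completers | Aspirin completers | Shift |
|---|---|---|---|---|
| 100% | 100% | 100% | 100% | 0 |
| 95% | 100% | 92.4% | 94.3% | 1.8 for Aggrenox |
| 90% | 100% | 84.8% | 88.5% | 3.7 for Aggrenox |
| 90% | 90% | 90% | 90% | 0 |
| 90% | 75% | 97.7% | 92.2% | 5.5 against Aggrenox |

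For example, (0.90 - 0.34)/0.66 = 84.8% and (0.90 - 0.13)/0.87 = 88.5%. With half the loss (17% and 6.5%), the two non-zero shifts at 90% become 1.4 for and 2.0 against.

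For scale, the standard error of the difference at 90% is √(0.09/16.5 + 0.09/21.75) = 9.8 points in completers, and √(2 × 0.09/25) = 8.5 points with 25 per arm.

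**Step 2: bias under the plan's own Aggrenox assumption.** A simulation used 95-100% flaring on aspirin, 50-65% on Aggrenox and 34%/13% withdrawal spread evenly over 24 weeks. Flare risk varied between patients (gamma frailty, variance 1). Withdrawal was unrelated to flare risk or linked to it (log-odds slope of ±1 per SD of log frailty). Bias is in aspirin minus Aggrenox, so a positive value favours Aggrenox.
- Completers: -8.7 to +7.5 points, and zero when withdrawal is unrelated to flare risk.
- Kaplan-Meier in all randomised patients: -3.3 to +2.7 points.

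A hand check agrees. With aspirin at 100%, only the Aggrenox arm can shift, and it shifts by *w*/(1 - *w*) = 0.34/0.66 = 0.515 times (*f* - *q*). If *f* = 65% and *q* = 80%, the completer rate is (0.65 - 0.272)/0.66 = 57.3%, which is 7.7 points too low. If *q* = 48%, it is (0.65 - 0.163)/0.66 = 73.8%, which is 8.8 points too high.

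**Step 3: flares left out.** Assume that everyone flares by day 168, that 72 days is an arithmetic mean, and that withdrawal is even over 24 weeks and independent of flare. Then the share of withdrawers who have already flared is 1 - 72/168 = 57%. That is 3.25 × 0.571 = 1.9 aspirin flares, and 8.5 × 0.571 = 4.9 Aggrenox flares if Aggrenox follows the same pattern. If all withdrawal falls in the first 8 weeks, the share can be anywhere from 0 to 57%, depending on how flare times are distributed. At 100% flaring these omissions lose data without biasing the rate.

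**The case against.** The best defence is that little hangs on this comparison. The primary is intention-to-treat. The plan already looks to time to flare, which can count flares before withdrawal, as a more sensitive endpoint. Patients who flare are kept in the study. The 12-point threshold for a larger study concerns the response rate, not flares. All of this stands, and it is why the point is minor. It does not repair the flare-rate comparison, and the log-rank set and censoring still need stating.

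It can also be said that 34% and 13% are drug-discontinuation rates in a stroke trial and not a forecast of withdrawal here. That is correct. They matter only so far as patients who stop the drug also leave the study, so every figure built on them is illustrative. The count of omitted flares is more fragile still, since intolerance may act early and the 72 days may not be an arithmetic mean.

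A reader might draw either of two stronger conclusions, and the documents support neither:
- *The completer rule favours Aggrenox.* Because flared patients are meant to stay, those who leave may flare more or less often than those who remain. Both directions appear in the working.
- *The bias is negligible because BOLD patients all flared.* That needs both arms at or near 100%, whereas BOLD stands for aspirin only and the plan expects Aggrenox to be well below that.

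**Conclusion.** The point holds as a minor one. The text is clear: a secondary comparison is conditioned on an outcome that follows randomisation, and recorded flares are discarded. Confidence in that reading is high.

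Confidence in the size is not. The bias is zero if withdrawal is unrelated to flare risk, or if both arms flare at 100%. Under the borrowed 34%/13% loss it runs from 3.7 points for to 5.5 points against Aggrenox at 90% flaring in both arms with no true effect. It is about -9 to +8 points if Aggrenox flaring is 50-65%. These ranges rest on assumed withdrawal and an assumed link to flare risk. The documents give no basis for calling any value in them likely.

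**What to change.** In section E, replace the completer comparison with one in all randomised patients that counts every flare observed before withdrawal. Report the Kaplan-Meier flare probability at week 24 in each arm, and the difference with its confidence interval. Name the interval method in advance, because the usual Greenwood interval fails if an arm reaches 100%. State the same analysis set, with censoring at withdrawal, for the log-rank test. Keep the completer comparison as descriptive, with completer defined. Add one labelled sensitivity analysis that counts withdrawal before flare as a flare.

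The cost is a few sentences and a little analysis, with no new data. There are drawbacks. Kaplan-Meier still assumes uninformative withdrawal, so it reduces the bias and does not remove it. The sensitivity analysis can penalise the arm with more withdrawal. The estimate may be less favourable to Aggrenox. The Kaplan-Meier and sensitivity differences should not be presented as bounds on the treatment difference, since each applies one rule to both arms at once.

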RESEARCH PROTOCOL

Title of project: Dipyridamole Assessment for Flare REduction in SLE: The DARE study

Principal Investigator: [name]

Co-Investigator: [name]

Co-Investigator: [name], PhD

Co-Investigator: [name]

Co-Investigator: [name]

Co-Investigator: [name], PA-C

Consultant: [name].

Abstract

T cells in systemic lupus erythematosus (SLE) express an abnormal phenotype characterized by increased effector functions and deficient regulatory responses. Dipyridamole, a phosphodiesterase inhibitor extensively used in combination with low dose aspirin in secondary stroke prevention, has been proposed as a specific T cell directed treatment for SLE. Dipyridamole inhibits the calcium/calcineurin/NF-AT pathway in SLE T cells *in vitro* and abrogates expression of cytokines and costimulatory molecules, eventually also affecting B cell responses. Dipyridamole delays the emergence of lupus related pathology in lupus prone mice, but has not yet been studied in humans with SLE. We aim to investigate the efficacy of dipyridamole in the prevention of flares in SLE patients after withdrawal of background immunosuppressive medications. We will additionally evaluate the safety and tolerability of dipyridamole and its impact on quality of life measures in this population. Furthermore, the effect of dipyridamole on T and B cell biomarkers will be examined.

A. Specific aims

Primary objective: To examine the efficacy of dipyridamole/aspirin (Aggrenox, Boehringer Ingelheim Pharmaceuticals, Inc.) for flare prevention in patients with SLE as measured by the BICLA endpoint (improvement in disease activity compared to baseline without new flare or additional treatments).

Secondary objectives: To examine the effect of dipyridamole on:

1. Flare rate and time to first flare
2. Systemic response index (SRI) 4/5 at week 24, BICLA and SRI 4/5 at each month, SRI component analyses, CLASI and DIAL responses

3. Patient reported outcomes, including: health related quality of life (measured by the Lupus QoL, LupusPRO and the Short Form 36v2), fatigue (measured by the FACIT-fatigue score), sleep quality (measured by the Pittsburgh Sleep Quality Index (PSQI)) and depression (measured by the Center for Epidemiologic Studies Depression (CES-D) Scale)
4. Tolerability and safety

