The dipyridamole dose administered in mice (50mg/kg) by Kyttaris VC *et al* (7) is considered equivalent to 4mg/kg in humans (12), the dose routinely use for thromboprophylaxis in clinical practice (oral administration). Pharmacodynamic studies for the anti-inflammatory and T cell inhibitory effects of dipyridamole have however not been conducted in humans, not excluding the possibility of lower doses also being effective. Immediate release dipyridamole and an extended release formulation of dipyridamole (200mg) in combination with low dose aspirin (25mg) (Aggrenox, Boehringer Ingelheim Pharmaceuticals, Inc.) are available in the US market.

Dipyridamole at standard daily dosing (400mg daily) is often poorly tolerated, mainly due to dizziness, headache and abdominal distress. In the large ESPRIT study of the combination of aspirin and dipyridamole, rates of treatment discontinuation due to intolerance were substantial (34% in the dipyridamole plus aspirin group versus 13% in the aspirin alone group) (13), and similar rates were observed in the ESPS2 trial (14). In clinical practice, a titration scheme of dipyridamole at initiation could be used to try to resolve the problem of drug-induced headache (15).

In ESPRIT, patients allocated to aspirin and dipyridamole had fewer major bleeding complications than patients allocated to aspirin alone, though this finding was not significant (13). Moreover, an equal rate of minor bleeding complications between groups was found in both ESPRIT and ESPS2, and few major bleeding complications were reported in either group. Similarly, the ESPS2 showed no difference in the frequency of severe or fatal bleeding complications between the two groups (14). Thus, treatment with dipyridamole and aspirin is overall considered at least as safe as low dose aspirin.

Heart rate variability (HRV) is an easily obtainable electrocardiographic measure of vagus nerve activity in humans and has been inversely correlated with inflammatory markers (C-reactive protein and IL-6) in the general population (16) (please see attached protocol). Decreases in HRV have been demonstrated in a broad array of pathologic conditions, including lupus (17, 18). The relation of HRV with disease activity in lupus patients has not been conclusively examined. Similarly, no previous studies have addressed the effect of dipyridamole on HRV.

D. Research design and Methods

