8. Any other medical condition, whether or not related to lupus which, in the opinion of the investigator would render the patient inappropriate or too unstable to complete the study protocol
9. Inability or unwillingness to understand and/or sign informed consent

2. Identify sources of research material in the form of specimens, records or data.

The research information will consist of clinical assessment performed by the physicians, health assessment questionnaires filled by the patients, and blood and urine specimens collected at each visit.

3. Describe plans for recruitment and consent procedures to be followed.

a. Describe the location where consent is most likely to take place

Patients will be recruited at the lupus clinic at the Oklahoma Medical Research Foundation. Candidate subjects will have the purpose of the study explained to them, including the benefits, risks and options, will be provided with the consent form, and after questions have been answered, will be invited to participate. No study specific procedures will be performed until a participant completes the informed consent process and signs the IFC form.

b. Describe provisions for recruiting non-English speaking participants.
Only English-speaking persons will be recruited.

c. Describe measures to decrease coercion of participants

Participants will be allowed adequate time to review the consent and encouraged to discuss the study with other caregivers or family. An important element of the process will be the understanding by the patient that their decision to participate or not will not affect their access to medical care in the clinic. Employees and clinic staff will be excluded from participation.

4. Describe risks and assess likelihood and seriousness.

The study medication, extended release dipyridamole in combination with low dose aspirin (Aggrenox, Boehringer Ingelheim Pharmaceuticals, Inc.), is known to be generally well tolerated and has been tested in several large randomized controlled trials (4). Aggrenox was approved in 1999 for prevention of stroke and has been used safely and effectively in high risk populations for many years. The main adverse events described are headache (39%), but tolerance usually develops. Other common adverse events are abdominal pain (18%), dyspepsia (18%), nausea (16%) and diarrhea (13%).

5. Describe procedures for protecting against or minimizing potential risks.

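### Group A: the week-24 flare-rate comparison is limited to completers, a set fixed after randomisation, and should use all randomised patients

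*Combined protocol and SAP*

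**What the plan says.** The Secondary endpoints paragraph of section E sets the comparison: "Flare rates at week 24 compared between completers among treatment groups". Nothing in the protocol defines a completer or gives an all-randomised version of this proportion. The same paragraph lists a log-rank test of time to flare, with no completers restriction and no stated analysis set or censoring rule.

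The primary endpoint is handled differently. Section E states "The primary analysis will be an intention-to-treat two by two table", "with non-response attributed to patients who receive defined non-responder treatments and/or withdraw early". Both statements concern the primary BICLA analysis only.

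The first secondary objective in section A is "Flare rate and time to first flare".

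On follow-up, section D schedules visits "every 4 weeks until the completion of the study at week 24" for participants in general. Patients who flare may receive rescue treatment "but will continue the study as permanent nonresponders". No sentence says what happens to a patient who stops the capsules for intolerance.

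On tolerability, section C reports from an outside stroke trial that "rates of treatment discontinuation due to intolerance were substantial (34% in the dipyridamole plus aspirin group versus 13% in the aspirin alone group"). Section D adds a one-week titration, and the risk paragraph of section G says the study drug "is known to be generally well tolerated".

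**The concern.** Whether a patient completes is known only after randomisation and may depend on the assigned drug. Comparing completers therefore gives up the balance that randomisation provides, for an endpoint close to the trial's stated purpose of reducing flares. If more patients fail to complete on one arm, and their flare risk differs from that of the rest, the completers' rates can differ with no drug effect.

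There is also a plainer loss. A patient who flares in week 3 and later withdraws has a fully observed outcome, yet does not enter this proportion. The pilot would then report a primary result on everyone and a flare rate on a subset, and the two would describe different patients.

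**Working it through.** The plan gives no power or precision figure for flare rate. Its power table concerns BICLA response and is not in question. A two-sided pooled-variance formula with 25 per arm gives 0.845, 0.866, 0.895, 0.811, 0.865, 0.772 and 0.844, against the stated 0.84, 0.86, 0.89, 0.80, 0.86, 0.77 and 0.84.

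**Inputs from the protocol:** 25 per arm; 34% v 13% stopping drug (section C, outside trial, no time period given); mean time to flare 72 days (interval 43 to 91) and 100% flaring by 24 weeks in the earlier withdrawal study (section C).

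**Assumptions:** stoppers are non-completers; they stop at day 21; flare times are exponential given a patient's risk. Halved stopping rates are shown where they matter.

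1. *Patients left out.* 25 × 0.34 = 8.5 and 25 × 0.13 = 3.25, in total 11.75 of 50. This leaves 16.5 v 21.75. With halved rates, 4.25 v 1.625 are left out (5.9 in total).

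2. *Recorded flares dropped from the proportion.* The chance of a flare before day 21 is 1 − exp(−21/72) = 0.253. So 8.5 × 0.253 = 2.2 and 3.25 × 0.253 = 0.8.

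3. *Flares never seen, if stoppers also leave.* The chance of no flare by day 21 is 0.747. The chance of a flare in the remaining 147 days is 1 − exp(−147/72) = 0.870. So 8.5 × 0.747 × 0.870 = 5.5 and 3.25 × 0.747 × 0.870 = 2.1.

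4. *Precision at 85% flaring in both arms* (variance 0.85 × 0.15 = 0.1275).
   - Completers: √[0.1275 × (1/16.5 + 1/21.75)] = 0.117.
   - Completers, halved rates: √[0.1275 × (1/20.75 + 1/23.375)] = 0.108.
   - All randomised, if all are observed: √(2 × 0.1275/25) = 0.101.

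5. *Bias with no drug effect.* Give each patient a standard normal risk score z and a flare hazard of exp(0.7z)/mean. Let the log-odds of stopping rise (+1) or fall (−1) per unit of z, with overall stopping held at 34% v 13%. The values 0.7 and ±1 are assumptions. Integrating over z gives the completers' difference, Aggrenox minus aspirin:

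| Mean, days | Overall flaring | Flare-prone stop | Flare-resistant stop |
|---|---|---|---|
| 43 | 93% | −1.4 points | +1.4 |
| 72 | 85% | −2.5 | +2.5 |
| 91 | 80% | −2.9 | +2.9 |
| 240 | 52% | −3.6 | +3.6 |
| 72, rates halved | 85% | −1.1 | +1.4 |

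The bias is zero if stopping is unrelated to z, and zero if every patient flares.

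6. *What the fix may cost in contrast.* Suppose Aggrenox halves the flare hazard while taken and the effect ends on stopping at day 21, with no variation in z. Aspirin: 1 − exp(−168/72) = 0.903. On drug throughout: 1 − exp(−84/72) = 0.689. Stopped at day 21: 1 − exp(−157.5/72) = 0.888. All randomised to Aggrenox: 0.66 × 0.689 + 0.34 × 0.888 = 0.757. The difference is about 15 points in all randomised and 21 points in completers.

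**The case against.** The strongest reply concerns what completing means. Section D speaks of completing the study at week 24, and the interim analysis is triggered by patients who have completed the study. Patients who flare stay in, even on rescue treatment. Only the duration-of-participation statement, which speaks of 24 weeks of treatment, points the other way. On the study reading, a reader might infer that 34% v 13% is the expected non-completion here, but the documents do not support that. The figure is drug stopping in a stroke population, no titration is described for it, and no sentence says that stoppers leave. This part of the reply stands, and the counts in steps 1 to 3 are an upper illustration.

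The most obvious informative loss, patients leaving because they flared, is already closed by section D. What remains is mainly headache, dizziness and abdominal distress, and nothing in the protocol links these to flare risk. Early flares can still count in the log-rank test. These points stand too, and they keep the likely bias small.

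A pilot looking for a signal might also prefer completers. In the example of step 6, the pooled-variance formula gives power of about 28% for all randomised: (0.146 − 1.96 × 0.106)/0.104 = −0.60. For completers it gives about 39%: (0.214 − 1.96 × 0.128)/0.130 = −0.28. The two comparisons estimate different effects, however, and the completers' figure is trustworthy only if stopping is unrelated to flare risk. That is a reason to keep the analysis as a supplement, not to make it the only flare rate.

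**Conclusion.** The point holds in a limited form. The plan's only stated flare-rate comparison rests on a set fixed after randomisation, and it drops flares that were recorded. At the outside trial's rates, and only if stoppers leave or are classed as non-completers, that means 8.5 v 3.25 of 25 left out, 2.2 v 0.8 recorded flares unused, and a standard error of 11.7 instead of 10.1 points. Bias is about 2.5 points either way at 85% flaring under assumed links, against a standard error of about 12 points. It is nil at the 100% flaring seen in the earlier withdrawal study.

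Three stronger readings are tempting and are not supported.

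- *That the rule favours Aggrenox.* The sign depends on whether flare-prone or flare-resistant patients fail to complete, and the documents do not say.
- *That the bias is large.* A difference of 14.6 points follows if 60% flare overall and every non-completer flares: (0.60 − 0.34)/0.66 = 39.4% v (0.60 − 0.13)/0.87 = 54.0%. Both inputs are invented for the purpose, and the 60% sits far from the protocol's own 100%.
- *That time to flare shares the fault.* The completers wording is attached to flare rates only. Censoring at drug stop would be the reader's assumption, so no bias is claimed for the log-rank test.

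The primary endpoint is unaffected.

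**What to change.** In section E, make the main flare-rate comparison the proportion with a flare by week 24 among all randomised group A patients. Count every recorded flare, and use the Kaplan-Meier week-24 estimate so that patients lost without a flare contribute until last contact. This still assumes that loss is unrelated to flare risk. Define completer, and keep the completers comparison as a sensitivity analysis.

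In section D, if group A resumes after the interruption described in the January 2015 amendment, state that a patient who stops the capsules is asked to attend the visits already scheduled to week 24, as patients who flare do. Only this follow-up recovers the unseen flares. Stopping decisions, rescue treatment and the primary endpoint stay as they are.

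The cost is two or three sentences, plus off-drug attendance at existing visits by about 6 to 12 patients at the halved or full outside rates. The section E change also serves patients already enrolled, while the section D change helps only those still to be followed. The downside is dilution by off-drug time, about 15 v 21 points in the example, which is why the completers analysis is kept.
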